Baseline patient characteristics will be evaluated with an interview adapted from our previous pain and fibromyalgia trials and will include socio-demographics, disability compensation, comorbid medical and psychiatric disorders, and prior treatments for fibromyalgia. We will also regularly assess use of other treatments for fibromyalgia (other medications, exercise, physical therapy, complementary and alternative medicine modalities, and interventional modalities) as well as prescription medication use. For medications, we will record prescribed doses, administration schedule, and number of pills prescribed, especially opioid analgesics, antidepressants, and benzodiazepines.

D8c. Description of Specific Measures

Fibromyalgia symptom severity will be assessed with the **Fibromyalgia Impact Questionnaire Revised (FIQR)**.⁹

Pain-severity: The Brief Pain Inventory is an 11-item, multidimensional pain measurement tool with demonstrated reliability in patients with arthritis as well as other pain conditions.^{102,103} The BPI rates the intensity of pain as well as the interference of pain with mood, physical activity, work, social activity, relations with others, sleep, and enjoyment of life.

Psychological symptoms are frequently associated with fibromyalgia and will be assessed by:

The PHQ-9 will be used to assess depression severity. Several studies have validated the PHQ-9 as a diagnostic measure with excellent psychometric properties.¹⁰⁴ Internal consistency has consistently been shown to be high (Cronbach's alpha > 0.80) and test-retest assessment showed the PHQ-9 to be a responsive and reliable measure of depression treatment outcomes.

The GAD-7 has demonstrated reliability (alpha = 0.89) and validity (criterion, construct, factorial, and procedural) as a measure of anxiety in the general population and primary care.¹⁰⁵

The Primary Care PTSD Screen (PC-PTSD) has been validated for use in VA primary care settings.¹⁰⁶ The sum of the 4 yes/no items yields a score ranging from 0 to 4, with scores ≥ 3 considered positive for active PTSD. Sensitivity is 78% and specificity is 87% compared to clinician interview.¹⁰⁷ In participants who screen positive, the PTSD Checklist for Military (PCL-17) will be administered. This 17-item scale assesses the DSM-IV symptoms of PTSD, and is used for diagnosis and as a severity measure as a measure of change in PTSD symptoms as a function of treatment. The PCL has demonstrated sensitivity and specificity >70%.¹⁰⁷

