Table . Outcome Assessment Protocol: Measures and Schedule of Administration

Domain	Measure	Items	Time (min)	Schedule				
				BL	1 mo	3 mo	6 mo	9 mo
Covariates	Demographics; contact information; disability compensation, comorbidity; pain treatments	36	10	X				
Fibromyalgia severity	Fibromyalgia Impact Questionnaire Revised	21	6	X	X	X	X	X
Pain Severity	Brief Pain Inventory	10	3	X	X	X	X	X
Psychological	PHQ-9 Depression	9	2	X		X		X
	GAD-7 Anxiety	7	2	X		X		X
	VA PTSD Screener	4	1	X		X		X
	VA PTSD Checklist (PCL-17)	17	4	X		X		X
Generic HRQL	Medical Outcomes SF-12	12	4	X		X		X
Fatigue	Multidimensional Fatigue Inventory	20	5	X	X	X		X
Sleep	MOS Sleep Scale	12	3	X	X	X		X

Pain beliefs	Pain Catastrophizing Scale	10	3	X		X		X
Pain coping	Centrality of Pain Scale	10	3	X		X		X
Self-efficacy	Arthritis Self Efficacy Scale	6	2	X		X		X
Treatment Response	Global Rating of Change	1	1		X	X	X	X
Physical Function and Activity	Functional Assessment which includes Fullerton Advanced Balance Scale (FAB)	18	10	X		X	X	
	Rapid Assessment of Physical Activity	8	2	X		X		X
	Activity Constraints	20	5	X		X		X
	Activities - Specific Balance Confidence Scale (ABC)	16	5	X		X		X
	Balance	7	2	X	X	X	X	X
Coherence	Sense of Coherence Scale	3	1	X		X		X
Substance Use	Illicit use and personal/family history	6	2	X				
Perceived Expectations	EXPECT Questionnaire	26	8	X	X			

Other secondary outcome measures and potential predictors of treatment response will be assessed:

The Medical Outcomes Study Short Form Questionnaire (SF-12) is the criterion standard for generic functional status and health-related quality of life.¹⁰⁸ The SF-12 assesses physical and mental functioning in 8 domains and gives reliable, valid and responsive summary scores.¹⁰⁸

The Multidimensional Fatigue Inventory (MFI) will be used to assess fatigue.¹⁰⁹ The MFI assesses clinical fatigue in 5 dimensions: general fatigue, physical fatigue, mental fatigue, reduced motivation, and reduced activity. The MFI has been validated among adults with chronic illness, chronic fatigue syndrome, and cancer, as well as among healthy adults.¹¹⁰

Sleep problems will be assessed using the MOS Sleep Scale which assesses sleep disturbance, adequacy of sleep, and sleep quantity. The MOS-Sleep Scale has demonstrated good psychometric properties in trials assessing pain.¹¹¹

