cognitive behavioral relaxation techniques and found a 13.6% reduction in FIQR scores. From these studies, we estimate the difference between the yoga and structured exercise group is 17%. A between-group treatment difference of 14% reduction in symptoms represents a minimum clinically meaningful intervention effect.¹¹⁹ To be conservative, we will assume a 14% difference between treatment groups. The absolute score difference at 3 months is estimated to be approximately 7 points (6.79, 14% of 48.3). Assuming a common standard deviation of 17.6 and using a two-sample t-test, we will need 107 evaluable subjects in each arm to detect such a difference with >80% power and 5% Type I standard error rate.

We recognize the correlation of outcomes from subjects within the same yoga or exercise class may reduce the effective sample size compared to the same sample with independent observations. This possible “clustering effect” seen in group delivered interventions has implications for power. We have no preliminary data to estimate the intra-cluster correlation (ICC) for participants within the same group. However, based on similarly designed published studies, we expect the ICC to be relatively small and balanced across the two treatment arms since the cluster sizes will be similar.¹²⁰ Conservatively, we assume an ICC of 0.02 for both treatment groups. With 8 subjects per treatment group/class or cluster, the design effect is $1 + (8-1) \times 0.02 = 1.14$. Therefore, we will inflate our sample size by 14% to accommodate the potential clustering effects. We then need 122 evaluable subjects in each arm. With a conservative 20% attrition, we will then need $(122 \times 2) / 0.80 = 306$ subjects (153 in each arm).

D9b. Data analysis: Baseline characteristics of POYSE sample

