Since POYSE is not specifically powered for the secondary outcome, these results should be interpreted cautiously unless they are highly significant ($p < .001$). Pain severity as assessed by the Brief Pain Inventory will be analyzed using a repeated measurement ANCOVA model in the same way as the FIQR total score. BPI measurement at 1, 3, 6, and 9 months will be used as the response variable. Main predictors will be intervention group, time (categorical), and their interaction adjusted for the baseline BPI score. A random intercept of subject effect will be used to accommodate correlation within subject. Another random intercept of either a specific yoga or exercise group will be used to accommodate correlation within group (clustering effect for group delivered intervention).

Psychological symptoms: PHQ-9 score, GAD-7 will be analyzed using a repeated measurement ANCOVA model in the same way as the FIQR total score with repeated outcomes at 1, 3, 6, and 9 months as the response variables, the same set of main predictors and adjusted for baseline outcome measurement. The PTSD screening status will be analyzed using a generalized linear mixed model with a logit link. The main predictors will be intervention group, time (categorical) and their interaction adjusted for baseline PTSD screening status. PTSD severity from PTSD checklist for military will be analyzed similarly.

Other secondary outcome measures: The analytical strategy for other outcomes will be similar to the FIQR total score. These outcomes include SF-36, MFI, MOS Sleep Scale, Pain Catastrophizing Scale, Arthritis Self-Efficacy Scale, and PGIC.

We will employ several secondary analyses to assess the effectiveness of the treatment arms compared to each other in improving:

- Individual fibromyalgia symptoms (pain, fatigue, sleep quality, function)
- Health-related quality of life
- Patient global impression of change
- Pain beliefs and self-efficacy

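### PTSD is analysed in the full sample only as screen-positive or not, although the 0–4 score is collected; modelling the score would be a cheap gain on a minor secondary outcome

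*Combined protocol and SAP*

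**What the plan says.** Section D8c describes the PTSD screen: "The sum of the 4 yes/no items yields a score ranging from 0 to 4, with scores ≥ 3 considered positive for active PTSD". The outcome assessment table schedules it at baseline, 3 and 9 months.

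Section D9e then specifies "The PTSD screening status will be analyzed using a generalized linear mixed model with a logit link". The model has arm, categorical time and their interaction, and is "adjusted for baseline PTSD screening status". The 0–4 score appears in no planned analysis, either as outcome or as covariate.

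The only finer PTSD measure is conditional on the screen. Section D8c states "In participants who screen positive, the PTSD Checklist for Military (PCL-17) will be administered". The assessment table lists the checklist at baseline, 3 and 9 months without repeating that condition, but nothing withdraws it. Its analysis is covered by one sentence in D9e: "PTSD severity from PTSD checklist for military will be analyzed similarly". This does not settle whether the logit model or the ANCOVA is meant.

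In the same paragraph of D9e, PHQ-9 and GAD-7 are analysed as scores by repeated-measures ANCOVA. For the FIQR, the yes/no responder analysis (D9d) is secondary to the analysis of the score (D9c).

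**The concern.** Cutting a five-level score at 3 discards information twice. In the outcome, a patient who goes from 2 to 0 counts as unchanged. In the covariate, baseline scores of 0, 1 and 2 are treated as equal, and so are 3 and 4. Section D9c justifies ANCOVA by the power gained when baseline and follow-up are correlated, and a coarse baseline gives part of that gain back.

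The support offered for the cut in D8c is sensitivity and specificity against clinician interview. That supports using it to screen. It does not bear on how well the cut registers change under treatment.

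The checklist does not supply a full-sample alternative, because it is given only to patients who screen positive. If that condition applies at follow-up, its analysis set is also chosen by a result obtained after randomisation.

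At stake is the precision of one secondary comparison of YOGA with SEP. The primary outcome, its analysis and the sample size are unaffected.

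**Working it through.** **1. The plan's own figure.** Section D9a gives the only power calculation, for the FIQR at 3 months: difference 6.79, SD 17.6, "with >80% power and 5% Type I standard error rate". Sidedness is not stated, so two-sided is assumed.

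- Standardised effect: 6.79 / 17.6 = 0.386 SD.
- Normal approximation: n = 2 × (1.96 + 0.842)² × (17.6 / 6.79)² ≈ 105.5, that is 106 per arm. The exact t-test gives 107, with power 80.2%.
- Clustering: 1 + 7 × 0.02 = 1.14, and 107 × 1.14 = 122.
- Attrition: 122 × 2 / 0.80 = 305, or 153 per arm, which is 306.

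The figure reproduces. For PTSD the same effective size is used: 122 / 1.14 = 107 per arm.

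**2. What has to be assumed.** The documents give no PTSD prevalence, baseline-to-follow-up correlation, item structure or expected effect. The simulations therefore varied:

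- the share screening positive at baseline, 20% to 50%;
- the shift between arms on the latent trait, 0 to 0.5 SD, with 0.386 SD borrowed from the FIQR only as a reference point;
- the latent correlation, 0.6 in the first model and 0.4 to 0.75 in the second.

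Each run analysed one follow-up visit. Logistic regression of score ≥ 3 on arm and baseline status was compared with ANCOVA of the 0–4 score on arm and baseline score.

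**3. First model: four yes/no items driven by one trait (loading 0.8, correlation 0.6), two-sided 5%, 2,000 runs per cell.** Power at 0.386 SD:

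| Screen-positive | Status | Score | Gain (points) |
|---|---|---|---|
| 20% | 40.9% | 66.7% | 25.8 |
| 30% | 51.5% | 72.7% | 21.2 |
| 40% | 56.9% | 74.1% | 17.2 |
| 50% | 58.7% | 74.3% | 15.6 |

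- At 0.25 SD, score against status ran from 35% vs 20% to 40% vs 31%.
- At 0.5 SD, it ran from 86% vs 59% to 92% vs 80%.
- With no effect, both methods rejected in 4.4–5.9% of runs.

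**4. Second model: a latent normal score cut directly into 0–4.**

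- With 30–50% positive, correlation 0.4–0.6 and effects of 0.2–0.386 SD, the gain was about 6 to 25 points.
- With 20–50% positive and correlation up to 0.75, it was about 6 to 40 points.
- If only baseline positives benefit (by 0.8 SD), the gain was 8 to 12 points.

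**5. Small effects (first model, 1,500 runs).**

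- At 0.15 SD: 17.3% vs 13.1% with 30% positive, and 16.3% vs 13.1% with 50% positive.
- At 0.10 SD: 9.8% vs 8.3%, and 9.7% vs 7.7%.

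The gains in these four cells are 1.5 to 4.2 points. Over 20–50% positive, the range at 0.15 SD or less is about 2 to 6 points.

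**6. The plan's stricter thresholds.** Sections D9e and following call for cautious reading unless p < .001, and for Bonferroni adjustment with fewer than 20 tests. The strictest Bonferroni case is 0.05 / 19 = 0.0026.

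- First model, 0.386 SD, at 0.0026: score against status 25% vs 7% (20% positive) to 35% vs 19% (50% positive).
- First model, 0.386 SD, at .001: 22% vs 8% (30% positive) and 24% vs 12% (50% positive).
- First model, 0.25 SD, at .001: 4–6% vs 2–3%.
- Second model, 0.386 SD, at 0.0026: 35–71% vs 10–30%. The score passed 50% only with a correlation of 0.6 or more.

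**The case against.** **PTSD is peripheral.** Aim 2 and the secondary hypotheses name depression and anxiety, not PTSD, and D9e says that the trial is not powered for secondary outcomes. This stands, and it sets the severity. It does not justify discarding information already collected.

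**The status is a legitimate, readable endpoint.** The instrument is a screener validated in VA primary care, and an odds ratio for screening positive is easier to interpret than a mean difference on four yes/no items. This stands as a reason to keep reporting the percentage positive. It does not require the cut to be the only full-sample analysis.

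**The checklist covers part of the gap.** A reader might infer that every within-category move is lost, including 4 to 3. The documents do not support that: such a patient is positive at both visits, so receives the 17-item checklist, and D9e plans an analysis of it. The uncovered loss is mainly movement below the cut and the coarse baseline covariate.

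**The size is not a property of the plan.** A reader might take one simulated range, such as the 9 to 27 points spanned by step 3, as what this trial loses. It depends on assumed prevalence, item structure, correlation and effect, and other reasonable inputs give anything from about 2 to about 40 points. The direction is steadier: the score had more power in every non-zero-effect cell tried.

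**The simulations are simplified.** They use one visit, and allow for clustering only through the effective sample size, while the plan specifies a mixed model with time and interaction. This stands; the figures indicate size and do not predict it.

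**Conclusion.** The point holds as a low-severity, inexpensive improvement. In the full randomised sample, PTSD is analysed only as a cut score adjusted for the same cut at baseline, although the uncut score is collected at every visit where the screen is scheduled.

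Assuming 107 effective patients per arm, two-sided 5% and 20–50% screening positive, the status analysis gives up roughly 5 to 30 points of power for latent effects of 0.25–0.5 SD. A wider grid with stronger correlation reaches about 40. At 0.15 SD or less the difference is about 2 to 6 points, and neither analysis would detect much.

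A reader might infer that the change would make the PTSD comparison adequately powered. That does not follow. At the multiplicity-adjusted thresholds, power is low for both analyses in the item-level model at 0.386 SD and below; only favourable settings of the second model take the score past one half. Nor does the point show bias: type I error was near 5% for both methods.

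**What to change.** In D9e, replace the sentence on PTSD screening status with a model of the 0–4 screen score at 3 and 9 months. Either a cumulative-logit mixed model or the repeated-measures ANCOVA already used for PHQ-9 and GAD-7 would serve. Include arm, visit, arm-by-visit, the baseline 0–4 score, and the patient and class random intercepts. Report the percentage screening positive by arm as a supportive summary. While editing, state which model the checklist sentence refers to and which patients enter it.

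The cost is a sentence or two of analysis text, with no new data or visits. The downside is that the effect becomes a common odds ratio or a score difference, which is less directly clinical than an odds ratio for screening positive. The reported percentages keep that reading available.

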Analytic techniques will be similar to those previously described. Since there will be a number of secondary outcomes, we will account for multiple-comparisons in analyses. We will use the Bonferroni approach to adjust for statistical significance threshold when the number of tests is less than 20. Otherwise, we will use the false discovery rate (FDR)¹²² to control the magnitude of false positives. We will also stratify our analysis based on a baseline depression status (PHQ-9). Our previous research indicated that 30% to 40% of patients will have clinically significant depression, which may adversely affect pain outcomes. Thus, depression is a potential moderator.

D9f. Missing data

Missing data are unavoidable in longitudinal studies. Based on our prior studies, we anticipate a possible dropout rate between 8% and 12%. However, we conservatively estimated a possible 20% drop out rate which is reflected in the sample size calculation. We will first run a logistic model with missing status as the response variable, intervention arm, patients’ demographic characteristics as covariates to check whether the missing status depends on the intervention group assignment and patient characteristics. Second, our linear mixed-effect model can accommodate missing-at-random (or

MAR which is assumed in many trials)¹²³ where no bias will be introduced by ignoring the missing-data mechanism. If drop-outs are Missing Not At Random (MNAR), meaning the likelihood of drop-out depends on an un-observed outcome, and the missing data mechanism is ignored, potential bias can be introduced. We will run sensitivity analyses using complete cases, last observation carried forward imputation, other multiple imputation methods including linear mixed-effect model, to compare results across these analyses to assess the robustness of the inference.

D9g. Economic evaluation

We will conduct cost effectiveness to determine if changes in health care utilization may offset the intervention costs between treatment arms. To conduct this analysis, we will use established methods¹²⁴ to estimate direct costs of the interventions and health care spending for study participants during the **9 month** trial period from the perspective of the VA.

D9h. Costing

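### The secondary-outcome rule switches from Bonferroni to FDR at 20 tests, but the plan never defines a test, and its named outcomes can fall on either side of 20

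*Combined protocol and SAP*

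**What the plan says.** Section D9e commits to adjustment: "Since there will be a number of secondary outcomes, we will account for multiple-comparisons in analyses". It then gives one rule with two branches. Below the cut: "We will use the Bonferroni approach to adjust for statistical significance threshold when the number of tests is less than 20". At 20 tests or more the FDR is used, with a literature reference but no FDR level and no named procedure in the text.

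The same section names the outcomes:

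- **Pain:** "BPI measurement at 1, 3, 6, and 9 months will be used as the response variable".
- **Depression and anxiety:** "PHQ-9 score, GAD-7 will be analyzed using a repeated measurement ANCOVA model", also with four post-baseline visits.
- **PTSD:** "The PTSD screening status will be analyzed using a generalized linear mixed model with a logit link", and "PTSD severity from PTSD checklist for military will be analyzed similarly".
- **Others:** a general health status form, the fatigue inventory (MFI), the MOS Sleep Scale, pain catastrophizing, arthritis self-efficacy and the global impression of change, all to be handled much as the FIQR total score is.

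D9e also plans analyses stratified by baseline depression. D9d adds a responder analysis and the three FIQR domains. Earlier in D9e, because the trial is not powered for secondary outcomes, the reader is told that "these results should be interpreted cautiously unless they are highly significant", with p < .001 given in brackets.

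**The concern.** The number of tests is the only input to the branching rule, and it is not defined. An adjustment rule is useful only if it can be applied in one way before the results are known. Here two analysts could follow D9e faithfully, count differently, and use different procedures on the same p-values.

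The two procedures also control different things. Bonferroni limits the probability of any false positive in the family. FDR limits the expected share of false positives among the results declared positive. The two error rates coincide when no outcome differs between arms, and can diverge once some do.

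At stake are the claims under Aim 2 and the secondary hypotheses: pain, sleep, fatigue, function, quality of life, depression and anxiety.

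**Working it through.** The plan states neither a number of tests nor an FDR level, so there is no figure of its own to reproduce on this point. The check is to count tests under each reasonable reading and see which branch applies.

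**Inputs.** Outcomes come from D9e. Scheduled post-baseline visits come from the outcome assessment table in D8c. The FIQR domain and responder analyses come from D9d. The 0.05 level and Benjamini-Hochberg (BH) are assumptions.

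**Step 1: one test per instrument, 3 months only.** BPI, PHQ-9, GAD-7, PTSD screen, PTSD checklist, SF form, MFI, sleep, catastrophizing, self-efficacy and global change make 11. If the SF form gives two summary scores (D8c mentions summary scores without a number), the count is 12. Both are below 20, so Bonferroni applies.

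**Step 2: instrument by scheduled visit.** In the same order: 4 + 2 + 2 + 2 + 2 + 2 + 3 + 3 + 2 + 2 + 4 = 28. With two SF scores it is 28 + 2 = 30. Both select FDR.

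**Step 3: instrument by the four visits that D9e writes for BPI, PHQ-9 and GAD-7, extended to all.** 11 × 4 = 44, so FDR applies.

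**Step 4: 3 months only, with subscales.** Start from 12. Replace the single MFI test by its five dimensions (D8c): 12 − 1 + 5 = 16. Add the three FIQR domains and the responder analysis: 16 + 4 = 20. That is no longer below 20, so FDR applies without counting any other visit. The depression strata could add more.

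**Step 5: effect on the cut-offs.** Bonferroni uses 0.05/m for m tests. BH compares the i-th smallest p-value with 0.05 × i/m.

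| Count m | Branch | Cut-off |
|---|---|---|
| 11 | Bonferroni | 0.05/11 = 0.0045 |
| 12 | Bonferroni | 0.05/12 = 0.0042 |
| 19 | Bonferroni | 0.05/19 = 0.0026 |
| 28 | FDR | 0.0018 (first step) to 0.05 (last) |
| 30 | FDR | 0.0017 to 0.05 |
| 44 | FDR | 0.0011 to 0.05 |

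**Step 6: two example p-values.**

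- *p = 0.01.* It fails Bonferroni at 12, since 0.01 > 0.0042. Under BH at 30 the rank needed is 0.01 × 30/0.05 = 6, so it passes if six or more p-values are 0.01 or lower. At 28 the rank needed is 5.6, rounded up to 6. At 44 it is 8.8, rounded up to 9.
- *p = 0.003, with no other small p-value.* It passes Bonferroni at 12, since 0.003 < 0.0042. Under BH at 30 it must meet the first step, 0.0017, and fails. It also fails at 28 (0.0018) and at 44 (0.0011).

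The verdict therefore moves towards significance in one case and away from it in the other.

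**The case against.** The strongest reply is that the plan is more definite than this suggests. Instruments, visits and models are named in advance. D9e says the secondary outcomes are analysed in the manner of the FIQR total score, and D9c judges that score by a 3-month contrast. One 3-month contrast per instrument gives about 11 tests and selects Bonferroni. This is a sensible reading and may be the intended one, but it is not stated. D9c also evaluates early and sustained response, D9d looks at responder odds at each time point, and neither section settles the choice of subscale.

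Three stronger readings are tempting, and the documents do not support them.

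- *The plan sets three competing significance standards.* Bonferroni and FDR are two branches of one stated rule. The p < .001 remark is advice on interpretation linked to limited power, not a formal threshold. It is stricter than any Bonferroni cut-off the rule can give (0.0026 at 19 tests), but a result may pass an adjusted threshold and still be read with caution.
- *Adding tests always relaxes the standard.* The lone p = 0.003 shows the opposite. FDR is the more lenient branch only when several outcomes are positive together.
- *The sponsor means to choose the procedure after seeing the results.* Nothing in the text says so. The gap leaves room for a late choice but is not evidence of one.

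It is also fair to say that FDR is a legitimate method for a large family. The problem is the undefined switch between methods, not the use of FDR.

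**Conclusion.** The concern holds in a limited form. D9e makes the error criterion depend on a count that the plan leaves open. The named outcomes give 11 or 12 tests at 3 months, 20 at 3 months with MFI dimensions and the FIQR analyses included, and 28 to 44 when visits are counted. Which branch applies is therefore not settled before the results are known.

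That the counts fall on both sides of 20 depends only on the document's own lists and schedule. The numerical cut-offs rest on a level of 0.05, and the FDR figures also on Benjamini-Hochberg. A different FDR level or procedure would change those figures, but the branch would still be undetermined.

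This is a desirable clarification, not a threat to the trial's main conclusion. The primary FIQR comparison at 3 months and the sample size, which is computed for that comparison alone, do not depend on it.

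**What to change.** Before arm comparisons are seen, amend D9e as follows.

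1. List the confirmatory secondary family, for example the 3-month arm contrast of each named outcome. State the scale or subscale for each: which MFI score, which SF summary score, and BPI intensity or interference. Give one name to the SF instrument, which is the SF-36 in D9e and the SF-12 in D8c.
2. Replace the count-dependent rule and plain Bonferroni with Holm at 0.05 for that family. With 12 tests the ordered cut-offs run 0.05/12 = 0.0042, 0.05/11 = 0.0045, and so on up to 0.05, stopping at the first failure. Holm controls the same family-wise error as Bonferroni and is never less powerful.
3. Report contrasts outside the family (other visits, further subscales, depression strata) with confidence intervals as supportive results.
4. Either keep the p < .001 remark, labelled as descriptive, or drop it.

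The cost is SAP wording, with no change to data collection or sample size. The trade-off is that results outside the listed family carry no confirmatory claim. If the team wants such a claim for a later visit, it should put that contrast in the family and accept smaller early Holm cut-offs.

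### The sensitivity analyses named in D9f do not vary the missing-outcome assumption by arm, so their agreement could give false reassurance about dropout missing not at random

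*Combined protocol and SAP*

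**What the plan says.** D9c makes the 3-month FIQR total score the primary contrast, taken from a repeated-measures mixed model with random intercepts for patient and for class. D9f says this model handles data that are MAR. It then names the case in which it fails: "If drop-outs are Missing Not At Random (MNAR), meaning the likelihood of drop-out depends on an un-observed outcome". If that mechanism is ignored, the section says, bias can follow.

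The response is the next sentence: "We will run sensitivity analyses using complete cases, last observation carried forward imputation, other multiple imputation methods including linear mixed-effect model". The results are to be compared with one another to judge how robust the inference is.

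D9f expects 8% to 12% dropout and uses 20% for the sample size. Two other checks bear on missingness: a logistic model of missing status on arm and demographics (D9f), and a comparison of baseline characteristics by dropout status and arm (D9b). D10e records reasons for withdrawal, but no described analysis uses them. The text supplied contains no delta-adjusted, tipping-point, pattern-mixture, selection-model or reference-based analysis.

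**The concern.** The plan names a specific threat and answers it with analyses that mostly share the primary model's assumption:

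- **Complete cases** need an assumption at least as strong as MAR.
- **Mixed-model imputation** repeats the primary model's MAR assumption, so close agreement with the primary result is nearly built in.
- **LOCF** is not a MAR method. It fixes a single assumption, no change after the last visit, and cannot be varied by size or by arm.

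The logistic model and the baseline comparison could flag unequal dropout, but they cannot detect dependence on scores that were never observed.

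The threat is plausible here. Participants are unblinded (D9). D7i says that patients with exercise-induced pain often abandon the programme. D7c ties attrition in earlier high-intensity studies to worsening symptoms and expects tailored yoga poses to reduce it. Symptom-driven dropout could therefore differ by arm, and it could bias the contrast in either direction. At stake is whether a reader can tell a fragile 3-month result from a sturdy one.

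**Working it through.** **Inputs (D9a and D9f).** Difference 6.79 points; SD and test as in "Assuming a common standard deviation of 17.6 and using a two-sample t-test"; operating characteristics "with >80% power and 5% Type I standard error rate" (taken as two-sided); ICC 0.02 with 8 per class; 153 per arm; dropout 20% for planning and 8% to 12% expected.

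**Step 1: reproduce the plan's sample size.** The exact power of the t-test is 0.798 with 106 per arm and 0.802 with 107, which matches "we will need 107 evaluable subjects in each arm to detect such a difference". The design effect is 1 + 7 × 0.02 = 1.14, and 107 × 1.14 = 121.98, which matches "We then need 122 evaluable subjects in each arm". Then 122/0.80 = 152.5, rounded up to 153 per arm, or 306 in total. The plan's figures hold. (14% of 48.3 is 6.762 rather than 6.79; this does not matter here.)

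**Step 2: tipping point.** Suppose the imputed 3-month scores of yoga dropouts are δ points worse than MAR predicts, and dropouts in the exercise arm follow MAR. With dropout proportion d, the yoga mean moves by d × δ and the benefit shrinks by the same amount. Holding the standard error fixed:

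- n = 153 × (1 − d) per arm
- SE = 17.6 × √(2 × 1.14/n)
- significance is lost at δ = (6.79 − 1.96 × SE)/d
- the whole difference is removed at δ = 6.79/d

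| Dropout | n per arm | SE | Lower 95% limit | δ at which significance is lost | δ that removes the difference |
|---|---|---|---|---|---|
| 20% | 122.4 | 2.40 | 2.08 | 10.4 | 34 |
| 12% | 134.6 | 2.29 | 2.30 | 19.2 | 57 |
| 8% | 140.8 | 2.24 | 2.40 | 30.0 | 85 |

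If both arms have the same dropout and the same δ, the shifts cancel (d × δ − d × δ = 0). Only a difference between arms matters.

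**Step 3: effect of baseline adjustment.** The plan gives no baseline correlation. Assuming 0.5, the SE falls by √(1 − 0.25) = 0.866. At 20% dropout it becomes 2.08, and significance is lost at (6.79 − 1.96 × 2.08)/0.20 = 13.6 points instead of 10.4.

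**Step 4: would the planned comparison reveal the problem?** A simulation used 153 per arm, 20% dropout after month 1, 600 runs and no class clustering. These inputs are assumed: within-patient correlation 0.5 or 0.7; dropout log-odds of 1 per SD of the unobserved 3-month score; half of any treatment difference present at month 1. A regression imputation stood in for the MAR methods. With a true difference of zero, the mean spurious benefit for yoga (range over the two correlations) was:

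| Dropout pattern | Complete case | MAR | LOCF |
|---|---|---|---|
| Worse scores drop out, yoga only | 1.6 to 2.2 | 1.3 to 2.0 | 0.7 to 1.2 |
| Opposite directions in the two arms | 3.2 to 4.5 | 2.7 to 4.0 | 1.4 to 2.2 |
| Same in both arms | about 0 | about 0 | about 0 |

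Complete-case and MAR estimates differ by only about 0.2 to 0.5 points, so they appear to confirm each other while sharing a bias.

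LOCF does separate from MAR, but the gap is ambiguous. With yoga-only MNAR dropout and no true effect it is 1.96 − 1.16 = 0.80 (correlation 0.5) or 1.31 − 0.70 = 0.61 (correlation 0.7). With dropout completely at random and a true effect of 6.79, it is 6.78 − 6.12 = 0.66 or 6.82 − 6.11 = 0.71. A gap of that size cannot tell the two situations apart.

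**The case against.** A reader might infer that nothing in the plan departs from MAR and that agreement would certainly mislead. The documents do not support that, for four reasons:

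- **LOCF is a departure from MAR,** and the reference to other multiple imputation methods is open-ended. It does not commit to an MNAR method, but it does not rule one out. The only method named, the linear mixed-effect model, is MAR.
- **Leaving classes is not the same as missing an FIQR score.** Outcomes are collected separately by a blinded assistant, in person or by telephone, with mailed questionnaires, clinic-visit interviews and taxi rides as back-up (D8). Participants who withdraw are asked to complete the remaining assessments (D10e). Dropout that follows a poor observed 1-month score is MAR, and the model covers it.
- **Expected losses are modest.** D9f anticipates 8% to 12%, and D4 reports 219 of 242 veterans (about 91%) assessed at 3 months in the team's earlier trial. At those rates the tipping deltas for a 6.79-point result exceed one SD (17.6).
- **Bias needs outcome-dependent dropout that differs by arm.** Both arms are weekly group programmes of the same length.

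It is also tempting to cite a borderline result. An observed 5.0 points at 20% dropout would tip at (5.0 − 1.96 × 2.402)/0.20 = 1.5 points. That mainly reflects a p-value already close to 0.05, and the plan does not target 5.0 points.

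All of this limits the size of the concern. None of it supplies an analysis that varies the missing-outcome assumption by arm, which is what the plan's own warning calls for.

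**Conclusion.** The concern holds as a gap in the sensitivity plan, not as a demonstrated bias. D9f raises MNAR dropout, and no analysis it names varies the assumption about missing outcomes by arm. Agreement could therefore be false reassurance if outcome-dependent dropout differs between arms; it need not be.

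For the design difference, the shift in yoga dropouts alone that overturns significance ranges from about 10 points at the conservative 20% dropout to 19 and 30 points at the expected 12% and 8%. These values rest on an observed difference of exactly 6.79, the D9a SD and design effect, no baseline adjustment (which would raise them) and an SE unaffected by the shift. The simulated biases also depend on the assumed correlation and dropout slope, so they illustrate the mechanism and do not forecast its size. The sample size is not in question. This is a change the sponsor should make, and it does not undermine the design.

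**What to change.** Add to D9f one prespecified delta-adjusted (pattern-mixture) multiple imputation analysis of the 3-month FIQR contrast:

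- Impute under MAR with the primary model's terms, keeping the class random effect.
- Shift the imputed scores over a grid of deltas fixed before outcome data are seen, applied to each arm separately.
- Report the delta at which the conclusion changes, next to the observed dropout in each arm and the team's prior view of what shift is plausible. The recorded withdrawal reasons can inform that view.

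LOCF may stay, but the text should say that agreement with it is not evidence of robustness to MNAR. It should also say which other imputation methods are meant.

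The cost is a paragraph of SAP text and a few extra runs of imputation already planned. No new data are needed, and the target stays at 306.
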